5.3. Eligibility for Optional Sleep Apnea Sub-Study

Subjects eligible for the main study will be eligible for the sleep apnea sub-study, if the following inclusion criteria are met:

- An apnea-hypopnea index (AHI) ≥ 5 events/hour based on polysomnography conducted prior to the first study period (Period I)
- Agreement to participate in the sub-study by signing a separate informed consent form

5.4. Screening/Baseline Failures

Screen failures are defined as subjects who consent to participate in the clinical trial but are not subsequently randomized. In order to ensure transparent reporting of screen failure subjects, meet the Consolidated Standards of Reporting Trials (CONSORT) publishing requirements, and respond to queries from Regulatory authorities, a minimal set of screen failure information is required including Demography, Screen Failure details, Eligibility Criteria, and any Serious Adverse Events.

5.5. Withdrawal/Stopping Criteria

The following actions must be taken in relation to a subject who fails to attend the clinic for a required study visit:

- The site must attempt to contact the subject and re-schedule the missed visit as soon as possible.
- The site must counsel the subject on the importance of maintaining the assigned visit schedule and ascertain whether or not the subject wishes to and/or should continue in the study.
- In cases where the subject is deemed 'lost to follow up', the investigator or designee must make every effort to regain contact with the subject (where possible, 3 telephone calls and if necessary a certified letter to the subject's last known mailing address or local equivalent methods). These contact attempts should be documented in the subject's medical record.
- Should the subject continue to be unreachable, only then will he/she be considered to have withdrawn from the study with a primary reason of "Lost to Follow-up".

[figure not shown]
A subject may withdraw from study treatment at any time at his/her own request, or may be withdrawn at any time at the discretion of the investigator for safety, behavioural or administrative reasons. If a subject withdraws from the study, he/she may request destruction of any samples taken, and the investigator must document this in the site study records. If a subject is withdrawn from study treatment, that subject will be withdrawn from the study.

5.5.1. Liver Chemistry Stopping Criteria

Liver chemistry stopping and increased monitoring criteria have been designed to assure subject safety and evaluate liver event etiology (in alignment with the FDA premarketing clinical liver safety guidance).

<http://www.fda.gov/downloads/Drugs/GuidanceComplianceRegulatoryInformation/Guidances/UCM174090.pdf>

Phase II Liver Chemistry Stopping and Increased Monitoring Algorithm

Liver Safety Required Actions and Follow up Assessments Section can be found in [Appendix 2](#)

5.5.1.1. Study Treatment Restart or Rechallenge

Study treatment restart or rechallenge after liver chemistry stopping criteria are met by any subject participating in this study is not allowed.

5.5.2. QTc Stopping Criteria

- The same QT correction formula must be used for each individual subject to determine eligibility for and discontinuation from the study. This formula may not be changed or substituted once the subject has been enrolled.
- For example, if a subject is eligible for the protocol based on QTcB, then QTcB must be used for discontinuation of this individual subject as well.
- Once the QT correction formula has been chosen for a subject's eligibility, the same formula must continue to be used for that subject for all QTc data being collected for data analysis. Safety ECGs and other non-protocol specified ECGs are an exception.
- The QTc should be based on single or averaged QTc values of triplicate electrocardiograms obtained over a brief (e.g., 5-10 minutes) recording period.

A subject who meets either of the bulleted criteria below will be withdrawn from the study:

- QTc > 500 msec OR Uncorrected QT > 600 msec
- Change from baseline of QTc > 60 msec

For patients with underlying **bundle branch block**, follow the discontinuation criteria listed below:

Baseline QTc with Bundle Branch Block	Discontinuation QTc with Bundle Branch Block
< 450 msec	> 500 msec
450 – 480 msec	≥ 530 msec

5.5.3. Other Dose Adjustment/Stopping Safety Criteria

For an individual study participant, additional stopping criteria include, but are not limited to:

- Significant changes to medication (e.g., diuretics) as judged by the Principal Investigator in consultation with the Medical Monitor if necessary
- An emergency room (ER) visit or hospitalization for treatment of an episode of acute decompensated heart failure (ADHF)
- Severe signs or symptoms or significant changes in any of the safety assessments (e.g., ECG, vital signs, laboratory tests) that put the safety of the individual at risk, as judged by the Principal Investigator in consultation with the Medical Monitor if necessary.

5.5.3.1. Troponin Stopping Criteria

If after screening, the local cardiac troponin (cTn) is > 2 times the subject's baseline value and > ULN for the assay, it is recommended that subject undergo repeat troponin testing and urgent evaluation if symptoms suggestive of cardiac ischemia are present.

Asymptomatic Subject:

If the second value of cTn is below the ULN for the assay or less than 2 times the subject's baseline value, the subject can continue in the study with close follow-up of symptoms. ECG and further cTn measurements should be performed as clinically indicated.

If the second value of cTn remains > ULN and > 2 times the subject's baseline value, treatment with GSK2798745 should be interrupted. The subject should be evaluated by a cardiologist and undergo any clinically appropriate testing. Any re-start of study treatment must be discussed with the GSK Medical Monitor.

Symptomatic Subject:

Cardiology consultation should be obtained immediately for any subject with new signs or symptoms suggestive of cardiac ischemia, including chest pain, increased shortness of breath, and diaphoresis. GSK2798745 should be discontinued permanently, and the subject should be withdrawn from the study.

5.5.3.2. Digoxin Stopping Criteria

For subjects who are taking digoxin, concentrations will be monitored prior to administration of study medication daily. If the digoxin concentrations are observed to be significantly lower or higher following study drug administration, the dose of digoxin may be titrated if possible in consultation with the Medical Monitor and Investigator. In case the digoxin dose cannot be titrated, the subject may be withdrawn from the study or continue in the study with the withdrawal of the digoxin treatment, as clinically appropriate. Any follow-up and safety observations will be collected and monitored in these subjects.

5.6. Subject and Study Completion

A completed subject is one who has completed all phases of the study including the Follow-up Visit.

The end of the study is defined as the last subject's last visit.

6. STUDY TREATMENT**6.1. Investigational Product and Other Study Treatment**

The term 'study treatment' is used throughout the protocol to describe the product received by the subject as indicated in the protocol design.

Study Treatment		
Product name:	GSK2798745	Placebo
Formulation description:	Granule filled capsule	Placebo blend filled capsule
Dosage form:	Capsule	Capsule
Unit dose strength(s)/Dosage level(s):	2.4 mg ¹	NA
Route of Administration	Oral	Oral
Dosing instructions:	Dose with 240mL water	Dose with 240mL water.
Physical description:	Size one White Opaque capsule containing white to almost white solid	Size one White Opaque capsule containing white to almost white solid
Method for individualizing dosage:	Pharmacy to assemble	Pharmacy to assemble

1. In the event of a dose adjustment, dosage levels for capsules filled with GSK2798745 granules will be accordingly adjusted.

6.2. Treatment Assignment

Subjects will be assigned to study treatment in accordance with the randomization schedule generated in RandAll NG by Clinical Statistics prior to the start of the study, using validated internal software.

Subjects will be randomized into the study by means of an interactive web response system (IWRS) i.e. RAMOS NG, to receive one the two treatment regimens shown below in [Table 1](#).

Table 1 Treatment Sequences

Sequence	Period 1	Period 2
AP	GSK2798745 2.4mg	Placebo
PA	Placebo	GSK2798745 2.4mg

6.3. Blinding

This will be a double-blind study where the sponsor and clinical pharmacist are unblinded and the following will apply.

- The investigator or treating physician may unblind a subject's treatment assignment **only in the case of an emergency** OR in the event of a serious medical condition when knowledge of the study treatment is essential for the appropriate clinical management or welfare of the subject as judged by the investigator.
- Investigators have direct access to the subject's individual study treatment via the IWRS (RAMOS NG).
- It is preferred (but not required) that the investigator first contacts the Medical Monitor or appropriate GSK study personnel to discuss options **before** unblinding the subject's treatment assignment.
- If GSK personnel are not contacted before the unblinding, the investigator must notify GSK as soon as possible after unblinding, but without revealing the treatment assignment of the unblinded subject, unless that information is important for the safety of subjects currently in the study.
- The date and reason for the unblinding must be fully documented in the CRF
- A subject may continue in the study if that subject's treatment assignment is unblinded by the discretion of the Investigator in consultation with the Medical Monitor.
- GSK's Global Clinical Safety and Pharmacovigilance (GCSP) staff may unblind the treatment assignment for any subject with a Serious Adverse Event (SAE). If the SAE requires that an expedited regulatory report be sent to one or more regulatory agencies, a copy of the report, identifying the subject's treatment assignment, may be sent to investigators in accordance with local regulations and/or GSK policy.

6.4. Packaging and Labeling

The contents of the label will be in accordance with all applicable regulatory requirements.

6.5. Preparation/Handling/Storage/Accountability

A description of the methods and materials required for preparation of GSK2798745 or placebo capsules will be detailed in a Technical Agreement. The capsules will be extemporaneously prepared as per instructions that will be reviewed and approved by GSK prior to use.

- Only subjects enrolled in the study may receive study treatment and only authorized site staff may supply or administer study treatment. All study treatments must be stored in a secure environmentally controlled and monitored (manual or automated) area in accordance with the labelled storage conditions with access limited to the

investigator and authorized site staff. Please see Study Reference Manual (SRM) for additional information regarding storage.

- The investigator, institution, or the head of the medical institution (where applicable) is responsible for study treatment accountability, reconciliation, and record maintenance (i.e. receipt, reconciliation and final disposition records).
- Further guidance and information for final disposition of unused study treatment are provided in the SRM.
- Under normal conditions of handling and administration, study treatment is not expected to pose significant safety risks to site staff. Take adequate precautions to avoid direct eye or skin contact and the generation of aerosols or mists. In the case of unintentional occupational exposure notify the monitor, Medical Monitor and/or GSK study contact.
- A Material Safety Data Sheet (MSDS)/equivalent document describing occupational hazards and recommended handling precautions either will be provided to the investigator, where this is required by local laws, or is available upon request from GSK.

Precaution will be taken to avoid direct contact with the study treatment. A MSDS describing occupational hazards and recommended handling precautions will be provided to the investigator. In the case of unintentional occupational exposure notify the monitor, Medical Monitor and/or GSK study contact.

6.6. Compliance with Study Treatment Administration

When subjects are administered study treatment at the study site, they will receive the treatment directly from the Investigator or designee, under medical supervision. The date and time of each dose administered in the clinic will be recorded. The dose of study treatment and study participant identification will be confirmed at the time of dosing by a member of the study site staff other than the person administering the study treatment. Study site personnel will examine each subject's mouth to ensure that the study treatment was ingested.

6.7. Treatment of Study Treatment Overdose

GSK does not recommend specific treatment for an overdose. The Investigator (or physician in charge of the subject at the time) will use clinical judgment to treat any overdose.

In the event of an overdose the investigator or treating physician should:

1. Contact the Medical Monitor immediately.
2. Closely monitor the subject for adverse events (AEs)/serious adverse events (SAEs) and laboratory abnormalities until GSK2798745 can no longer be detected systemically (at least 5 days for GSK2798745).

3. Obtain a plasma sample for pharmacokinetic (PK) analysis within 1 day from the date of the last dose of study treatment if requested by the Medical Monitor (determined on a case-by-case basis).
4. Document the quantity of the excess dose as well as the duration of the overdosing in the CRF.

Decisions regarding dose interruptions or modifications will be made by the investigator in consultation with the Medical Monitor based on the clinical evaluation of the subject.

6.8. Treatment after the End of the Study

The investigator is responsible for ensuring that consideration has been given to the post-study care of the subject's medical condition, whether or not GSK is providing specific post-study treatment.

6.9. Lifestyle and/or Dietary Restrictions

6.9.1. Monitoring in the Unit

The first six subjects who participate in the study will be admitted to the unit to be monitored for the first two days (Day 1 and Day 2) following the first administration of study medication in both study periods. Subsequently, these subjects will remain in the unit for a minimum of 4 hours after the administration of study medication on each of the remaining 5 days (Days 3 through 7) of each study period. On Day 5, subjects will remain in the unit for a minimum of 4 hours after the completion of the saline infusion.

For the remainder of subjects participating in the study, they will remain in the unit for a minimum of 4 hours after the administration of study medication on each of the 7 days of each study period.

Following the completion of all assessments on each study day, subjects may return home. For subjects who cannot return home each evening for multiple reasons including but not limited to distance from clinical site or transportation issues, housing will be provided or they may opt to remain in the unit for the duration of the study period. Housing should be consistent in both study periods. All subjects will be continuously monitored remotely (see Section 7.4.7).

6.9.2. Meal and Dietary Restrictions

Subjects are not permitted to consume red wine, Seville oranges, grapefruit or grapefruit juice and/or pummelos, exotic citrus fruits, grapefruit hybrids or fruit juices from 7 days prior to the first dose of study medication until their discharge from the unit after their last dose of study medication in each period.

Three meals per day will be provided by dietary department either in the unit or as a boxed meal(s) to go.

No meal restrictions will be placed with regard to drug administration. Subjects will be allowed to consume a standard breakfast prior to drug administration.

6.9.3. Caffeine and Alcohol

During each study period, it is recommended that subjects minimize ingestion of caffeine- or xanthine-containing products (e.g., coffee, tea, cola drinks, and chocolate) for 24 hours prior to the start of dosing until completion of all assessments.

During each study period, subjects will abstain from alcohol for 24 hours prior to the start of dosing until completion of all assessments.

6.9.4. Activity

Subjects should refrain from strenuous activity 48 hours prior to each study period and throughout the study (except when in the exercise portion of the study). Subjects may participate in light recreational activities during studies (e.g., watch television, read).

6.10. Concomitant Medications and Non-Drug Therapies

6.10.1. Permitted Medications and Non-Drug Therapies

Acetaminophen at doses of \leq 3 grams/day is permitted for use any time during the study.

The patients may stay on all regular prescription medications unless specified in Section 6.10.2. Digoxin is permitted, but with close monitoring to maintain the therapeutic window. Other concomitant medication may be considered on a case by case basis by the Investigator in consultation with the GSK Medical Monitor.

6.10.2. Prohibited Medications and Non-Drug Therapies

Except for the permitted medications noted above (Section 6.10.1), subjects must abstain from taking non-prescription drugs (including vitamins and dietary or herbal supplements), within 7 days (or 14 days if the drug is a potential enzyme inducer) or 5 half-lives (whichever is longer) prior to the first dose of study medication until completion of the follow-up visit, unless in the opinion of the Investigator and sponsor the medication will not interfere with the study.

Subjects must provide to the investigator information/list of all medications they are currently taking.

GSK2798745 has weak CYP3A4 inhibition potential. There is a likelihood that the concentrations of drugs that are substrates of CYP3A4 may be increased. HMG-CoA reductase inhibitors such as atorvastatin and simvastatin are examples of CYP3A4 substrates that are likely to be taken by the eligible patients as part of their medications. The concentrations of these statins will be monitored during the study. The investigators may also consider substitutions of these medications.

Subjects should avoid using drugs that are strong inhibitors or inducers of Cytochrome P450 (CYP) 3A4 or p-glycoprotein (P-gp) because they may alter GSK2798745 concentrations. The list of background therapy/drugs may be modified based on emerging data. These include, but are not limited to, those listed in Table 2; consider therapeutic substitutions for these medications.

GSK2798745 systemic concentrations will be monitored to detect any drug interactions with moderate CYP3A4 inhibitors or P-gP inhibitors (see SRM for a detailed list).

It is strongly recommended that patients avoid using drugs that are sensitive substrates of Cytochrome P450 (CYP) 3A4 and/or P-gp or that have a low therapeutic index because concentrations of these substrates may be increased by GSK2798745. If co-administration of medications with interaction potential with GSK2798745 is necessary, investigators should monitor subjects for loss of efficacy or consider substitutions of these medications. See SRM for a detailed list. The list may be modified based on emerging data. All concomitant medications may be reviewed by the Medical Monitor and it will be up to the discretion of the Investigator and if necessary the Medical Monitor, whether the medication can be continued and/or the subject can participate in the study.

Table 2 Strong inducers/inhibitors of CYP3A and P-gp

Antiretrovirals:	atazanavir, danoprevir, elvitegravir, fosamprenavir, indinavir, lopinavir, nelfinavir, ritonavir, saquinavir, telaprevir, tipranavir
Antibiotics:	clarithromycin, telithromycin, troleandomycin, rifampin
Oral antifungals:	ketoconazole, itraconazole, voriconazole
Antidepressant	nefazadone
Immunosuppressant	cyclosporine
Anti-Epileptic	carbamazepine, phenytoin

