7.5. Pharmacokinetics

7.5.1. Blood Sample Collection

Blood samples for pharmacokinetic analysis of GSK2798745 will be collected at the time points indicated in Section [7.1](#) Time and Events Table.

Approximately 2 mL of blood will be collected in EDTA tubes. The actual date and time of each blood sample collection will be recorded. The timing and volume of PK samples may be altered and/or PK samples may be obtained at additional time points to ensure adequate PK monitoring of GSK2798745 and, if possible, any relevant GSK2798745 metabolites.

Where possible, PK monitoring of relevant co-administered drugs and their metabolites will also be undertaken (atorvastatin and simvastatin). Approximately 2 mL of blood will be collected into sodium heparin tubes. The actual date and time of each blood sample collection will be recorded. The volume of such samples may be altered and additional time points may be added to ensure adequate statin PK monitoring.

Additional collection, processing, storage and shipping procedures are provided in the Study Reference Manual (SRM).

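### Protocol 6.10.2 predicts that GSK2798745 may raise substrate concentrations but, for necessary co-administration, names only loss of efficacy to monitor; the error matters only for substrates other than digoxin and statins

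*Protocol*

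**What the plan says.** Protocol Section 6.10.2 describes GSK2798745 as having weak potential to inhibit CYP3A4 and adds: "There is a likelihood that the concentrations of drugs that are substrates of CYP3A4 may be increased". Atorvastatin and simvastatin are given as likely examples, and "The concentrations of these statins will be monitored during the study".

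Later in the section, sensitive CYP3A4 or P-gp substrates and low-therapeutic-index drugs are to be avoided on strong recommendation, "because concentrations of these substrates may be increased by GSK2798745". Where such co-administration is necessary, the instruction is that "investigators should monitor subjects for loss of efficacy or consider substitutions of these medications". The reader is then sent to the SRM for a list. The Medical Monitor may review concomitant medications, and "it will be up to the discretion of the Investigator and if necessary the Medical Monitor, whether the medication can be continued".

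Section 6.10.1 lets patients keep their regular prescriptions unless Section 6.10.2 specifies otherwise, and leaves other concomitant medication to case-by-case consideration by the Investigator with the Medical Monitor. On digoxin it says: "Digoxin is permitted, but with close monitoring to maintain the therapeutic window". Section 5.5.3.2 requires daily pre-dose digoxin concentrations and continues: "If the digoxin concentrations are observed to be significantly lower or higher following study drug administration, the dose of digoxin may be titrated".

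**The concern.** The section predicts one direction of interaction and tells the site to watch for the consequence of the opposite direction. If the study drug raises the concentration of a co-medication, the patient is at risk of excess effect or toxicity from that co-medication. Loss of efficacy would be expected if its concentration fell. Nothing in the sentence asks the site to look for over-exposure.

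The situation it governs is one the protocol allows. Avoidance of substrates is recommended, not required, and exclusion criterion 15 in Section 5.2 covers strong inhibitors and inducers, not substrates as a class. Section 9.3.2 keeps all site personnel except the pharmacist blinded, so staff do not routinely know which period carries the interaction risk. A correct directional cue would be useful in both periods. What is at stake is subject safety, not the efficacy comparison.

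**Working it through.** No arithmetic applies. The check compares the direction of the predicted interaction with the direction of the monitoring instruction, then looks for other text that fills the gap.

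1. **Predicted direction.** Section 6.10.2 says twice that substrate concentrations may rise, and never that GSK2798745 may lower them. No section describes the drug as an inducer of CYP3A4 or P-gp. The digoxin rule in 5.5.3.2 acts on a change either way, but it does not predict a fall.

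2. **Instructed direction.** The sentence on necessary co-administration names one effect to monitor, loss of efficacy. Toxicity, adverse effects and substrate concentrations are not named there. The match fails.

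3. **Drugs covered elsewhere.**
   - Digoxin: Sections 6.10.1 and 5.5.3.2 give daily levels, with action on high as well as low values.
   - HMG-CoA reductase inhibitors: the exploratory endpoint in Protocol Section 3, Table 3 in Section 7.4.9 and the analysis text in Section 9.4.4 refer to the class. The sampling and assay text in Sections 7.5.1 and 7.5.2 names only atorvastatin and simvastatin. Exposure monitoring is therefore clear for those two and stated at class level for the rest.

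4. **Drugs not covered.** Table 3 lists co-medication concentration tests for digoxin and HMG-CoA reductase inhibitors only. Footnote 1 to the Time and Events Table allows some PK timepoints to serve other medications, but its examples are the same two statins. No other CYP3A4 or P-gp substrate is named for concentration monitoring.

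5. **General safeguards for the uncovered drugs.**
   - Severe signs or significant changes in safety assessments are individual stopping criteria (5.5.3).
   - Subjects stay in the unit at least 4 hours after each dose (6.9.1).
   - Vital signs are taken on every dosing day, and laboratory tests, including CPK, on Days 4 and 7 (7.1, Table 3).
   - ECG and heart rate are monitored continuously (7.4.7).
   - Sequelae of a suspected interaction count as adverse events (12.4.1), and causality assessment considers concomitant therapy (12.4.5).

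   None of these tells the site to look for over-exposure to a particular co-medication.

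The mismatch in steps 1 and 2 therefore stands. Steps 3 and 4 limit it to substrates other than digoxin and HMG-CoA reductase inhibitors, and step 5 reduces its consequence.

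**The case against.** The strongest reply is that the sentence is not the main safeguard. The paragraph first recommends avoidance and gives raised concentrations as the reason, so a physician reading it has just been told the direction. It offers substitution as an alternative to monitoring, and both 6.10.1 and 6.10.2 provide for review of individual medications. Sections 7 and 7.4 allow safety assessments to be added in the light of new data. The inhibition is described as weak, no affected subject or drug is identified, and the SRM may say more. All of this stands, and it keeps the consequence low. It does not make the sentence correct.

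A second reply is that medications with interaction potential could include drugs that lower GSK2798745 exposure, for which loss of efficacy would fit. The placement is against this. Drugs that alter GSK2798745 concentrations are handled in the preceding paragraphs with their own actions, and strong inducers are excluded. The sentence sits in the paragraph on substrates. Even on the wider reading, it omits the risk just stated.

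A reader might also infer something stronger: that the protocol has no monitoring for raised co-medication levels, or that patients on digoxin or statins were left unprotected. The documents do not support this. Digoxin has daily levels with action in both directions, statin concentrations are measured, and the general safeguards apply to everyone. Nor can it be said that sites lacked drug-specific toxicity guidance, because the SRM was not seen.

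**Conclusion.** The point holds as a wording error in a safety instruction that is in force: the only effect named for monitoring is opposite to the predicted interaction. Confidence is high for that mismatch. It does not extend to what sites were told in practice.

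The consequence is low. It reaches only subjects who continue, without substitution, a sensitive or low-therapeutic-index substrate other than digoxin or an HMG-CoA reductase inhibitor. The documents give no count, and it may be zero. The edge of the statin exception is uncertain for drugs other than atorvastatin and simvastatin, because the class-wide and two-drug texts differ. SAP Section 4.1 records a decision to enrol only one more patient, so a correction at that stage would help few subjects in this trial. No efficacy estimate or test depends on the sentence.

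The conclusion assumes that the sentence refers to the substrates named just before it, and that the SRM does not already supply the missing direction.

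**What to change.** In Section 6.10.2, change what is to be monitored when co-administration is necessary to: signs of increased exposure to, or toxicity from, the co-administered medication, and loss of efficacy where relevant. Keep the option to substitute. Because loss of efficacy is retained where it applies, the wording works under either reading of the sentence.

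Check any corresponding SRM text and align it. The cost is one protocol sentence and that check, with no added visit, sample or procedure.
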